#### Compensation

Compensation for study participation will be provided to each patient via Greenphire. Participants in aim 1 will receive \$20 for study participation and completion of the singular study visit. Participants in aim 2 may receive up to a total of \$60 for study completion, \$20 for each survey (T1, T2 and T3) to be paid after the participant has completed the trial.

#### 8. Enrollment Sites

This study will be conducted at Duke University Health (DUH) and Duke Regional Hospital (DRH).

It is anticipated that between both sites, the study team will enroll approximately 2/3 of their population from DUH (~40 patients) and 1/3 from DRH (~20).

## 9. Statistical Design, Analyses Plan, and Sample Size and Power

### Statistical Design and Analyses Plan

The primary goal of this 3-arm pilot RCT is to explore the feasibility and acceptability of mCST to inform a definitive future clinical trial. To do so, we will test differences between observed and a priori-defined benchmarks among mCST recipients using t-tests for continuous variables and chi-square tests for categorical variables.

The secondary goal is to estimate a reasonable range of clinical effect of mCST in comparison to a usual care control condition. General linear models will be used to estimate mean changes and corresponding 95% confidence intervals (CIs) in psychological distress (i.e., HADS and PTSS scores) for each treatment group over the 3 months of post-randomization follow-up using SAS PROC MIXED (SAS Institute, Cary NC). We will fit the models with an unstructured covariance matrix to better understand and represent the correlation between patients' repeated measures. We will also use similar modeling strategies to explore how the key clinical characteristics (e.g., history of ICU delirium, illness severity, diagnosis grouping), objective physical characteristics (e.g., functional status), sociodemographic factors, and mechanistic elements (e.g. self-efficacy) described in the conceptual model are associated with changes in psychological distress both within and between treatment groups. While for main analyses we will pool all mCST participants in comparisons with usual care control, we will also perform exploratory analyses similar to those described above to compare all three groups as well.

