#### **4. Study Objectives, Hypotheses, and Outcomes**

The overall objective of the pilot RCT is to determine the feasibility, acceptability and clinical impact of the intervention on patients' 1- and 3-month psychological distress symptoms of a self-directed mobile coping skills training (mCST) intervention, known as "Blueprint" as compared to usual care control.

The primary hypothesis in which this study is based is that the mCST will be feasible and acceptable based on comparison of observed to priori benchmarks.

The second hypothesis is compared to usual care, the mCST use by enrolled subjects will lead to improvement in symptoms of psychological distress via the HADS and PTSS at the 1- and 3-month mark post randomization.

The primary outcome of the pilot RCT is centered on acceptability and feasibility. The Client Satisfaction Questionnaire 8 will measure acceptability with open-ended participant feedback completed at the time of T3, which is considered end of study (EOS). Feasibility will be measured by frequency of randomization, retention, and adherence. Secondary outcomes are HADS and PTSS scores at 1 and 3 months post-randomization.

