3.1 Primary Outcome(s)

Variable	Dataset	Description	Specifications

hads	Blueprint/Baseline	HADS total score at T0	Continuous
Hads	Blueprint/T1	HADS total score at T1	Continuous (may need to be derived from item scores HADS01—HADS14)
Score_hads	Blueprint/T2	HADS total score at T2	Continuous (may need to be derived from item scores HADS01—HADS14)
Score_hads	Blueprint/T3	HADS total score at T3	Continuous (may need to be derived from item scores HADS01—HADS14)
ptss	Blueprint/T1	PTSS total score at T1	Continuous (may need to be derived from item scores ptss_1—ptss_10)
Score_ptss	Blueprint/T2	PTSS total score at T2	Continuous (may need to be derived from item scores ptss_1—ptss_10)
Score_ptss	Blueprint/T3	PTSS total score at T3	Continuous (may need to be derived from item scores ptss_1—ptss_10)
D3mo_HADS	Blueprint/T3 Blueprint/T1	Change in HADS at 3 months	Derived as Score_hads(T3) - ???
D1mo_HADS	Blueprint/T2 Blueprint/T1	Change in HADS at 1 months	Derived as Score_hads(T2) - ???
D3mo_PTSS	Blueprint/T3 Blueprint/T1	Change in PTSS at 3 months	Derived as Score_ptss(T3) - ???
D1mo_PTSS	Blueprint/T2 Blueprint/T1	Change in PTSS at 1 months	Derived as Score_ptss(T2) - ???
ADLs/IADLs	T1, t2, t3		Not really an outcome but...
Systems Usability Scale	T1		
PHQ-10 physical symptom scale	T1, t2, t3		
Quality of life 100-point VAS	T1, t2, t3		
List		Feasibility	
Eligibility: 70% of positive screens Consent: 80% of eligible Randomized: 80% of consented Retention: 80% Adherence: 75% of tasks
 
***note that these need to be defined a bit more specifically

CSQ-8	`	Acceptability	

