3.3 Other Variables of interest

Variable	Dataset	Description	Specifications

4 Statistical Analysis Plan

All analyses will be done using SAS 9.4. Continuous variables will be summarized with mean/standard deviation/median/Q1-Q3/range and categorical variables with frequency counts and percentages. Number of missing data for each variable will be reported.

4.1 Analysis Plan for Primary Aim 1

1. First, we will describe our cohort. In Table 1 we will summarize participant characteristics overall and by arm. No statistical tests will be provided as this was a randomized trial, and ideally groups should be balanced.
2. To assess Aim 1 for feasibility and acceptability we will evaluate CSQ-8 and SUS scores. Results will be reported in Table 2.

4.2 Analysis Plan for Primary Aim 2

1. To address Aim 2, we will describe the secondary outcomes at each time point by arm, as well as the change in scores at T2 and T3 from T1 in Table 3. Any additional secondary outcomes will be described in this table.
2. To assess if there was change at each timepoint of interest between the arms we estimate mean changes (and 95% CI) from baseline to each timepoint for each distress outcome (HADS, PTSS) using a general linear model (PROC MIXED). Model parameters will include treatment arm (1, 2, 3), time indicator (T1, T2, T3), and an arm by time interaction term. Change estimates and CI's will be reported in Table 4. To quantify clinically important differences, rather than report p-values which is not recommended for pilot studies with

small sample sizes, we will compare the estimated group mean differences and 95% CI's to half (0.5) of the baseline standard deviation (SD) of each outcome score.

5 Appendix I: Planned figures and tables

Figure 1: CONSORT Diagram

Table 1: Demographic characteristics of participants at baseline

Characteristic	Arm 1: Intervention Group 1 (Blueprint + Therapist) N=	Arm 2: Intervention Group 2 (Blueprint only) N=	Arm 3: Control (Usual Care) N=	Total N=
Stratification Variables				
Age				
<50				
≥50				
ICU Service				
Medical				
Surgical				
Baseline HADS				
<14				
≥14				
Other Baseline Characteristics				
Age				
Mean (sd)				
Median				
Q1, Q3				
Range				
Gender				
Male				
Female				

Table 2: Feasibility and Acceptability

Characteristic	Arm 1: Intervention Group 1	Arm 2: Intervention Group 2	Arm 3: Control (Usual Care)	Total N=

	(Blueprint + Blueprint Therapist) N=		N=
	N=	N=	
Feasibility			
% Consented	--	--	--

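### Feasibility, the primary question, is to be judged by tests of difference from benchmarks with no decision rule, in a population that cannot serve as denominator for the pre-randomisation rates

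*Protocol*

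**What the plan says.** Protocol section 4 makes feasibility and acceptability the primary outcome. Its primary hypothesis is that the app will be "feasible and acceptable based on comparison of observed to priori benchmarks". On what is measured it says "Feasibility will be measured by frequency of randomization, retention, and adherence".

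Protocol section 9 gives the method: "we will test differences between observed and a priori-defined benchmarks among mCST recipients", "using t-tests for continuous variables and chi-square tests for categorical variables". It states no alpha, sidedness, margin or rule for calling a benchmark met.

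The numerical benchmarks appear only in SAP 3.1: "Eligibility: 70% of positive screens", "Consent: 80% of eligible", "Randomized: 80% of consented", retention 80%, and adherence 75% of tasks. A note there says the definitions still need to be made more specific.

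SAP 4.1 then says "To assess Aim 1 for feasibility and acceptability we will evaluate CSQ-8 and SUS scores", with results in Table 2. That table has feasibility rows for consent, randomisation, retention, survey completion and completion of all intervention components. It has no eligibility row, benchmark column, confidence interval or criterion.

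**The concern.** The hypothesis asks whether benchmarks were reached. The planned test asks whether the observed rate differs from the benchmark, in either direction. Failing to find a difference in a small sample is weak evidence on whether the benchmark was reached. With no decision rule, a shortfall that misses significance could be described as consistent with the benchmark.

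The second problem is the population. Screening, consent and randomisation take place before anyone is an app recipient, so rates for those steps cannot be calculated among app recipients.

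At stake is the usefulness of the trial's primary result, which is meant to inform a definitive trial.

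**Working it through.** There is no stated power or precision figure to reproduce, because protocol section 9 describes the sample size as pragmatic. The check is therefore how the stated test would behave.

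**Inputs**
- Benchmarks: retention 80% and adherence 75% (SAP 3.1).
- App patients: 25 + 25 = 50 (protocol section 2). The SAP targets 15 + 15 = 30 (SAP section 2) but does not carry the test forward, so n = 30 shows only what would happen if the test were applied there.
- Alpha: not stated; two-sided 5% assumed.
- True rates: assumed, 65% to 75%.

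**Retention, non-significant range.** One-sample chi-square: X² = (x − n·p0)² / (n·p0·(1 − p0)), with p0 = 0.80 and critical value 3.84.
- n = 50: n·p0 = 40 and the divisor is 8. x = 34 gives 36/8 = 4.50 (significant); x = 35 gives 25/8 = 3.13 (not). By symmetry x = 45 is not significant and x = 46 is. Range: 35/50 (70%) to 45/50 (90%).
- n = 30: n·p0 = 24 and the divisor is 4.8. x = 19 gives 25/4.8 = 5.21; x = 20 gives 16/4.8 = 3.33. Range: 20/30 (67%) to 28/30 (93%).

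The exact binomial test gives the same ranges.

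**Chance of a non-significant result.** Sum of Binomial(n, p) over those ranges:

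| True retention | n = 50 | n = 30 |
|---|---|---|
| 75% | 0.83 | 0.89 |
| 70% | 0.57 | 0.73 |
| 65% | 0.28 | 0.51 |

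With alpha 10% (chi-square), the 70% row becomes 0.45 and 0.59.

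**Opposite reading.** If significance were required to pass, a programme truly at 85% would give a significant result in only 11.4% (n = 50) or 5.1% (n = 30) of trials.

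**Adherence.** As a proportion against 75%, results down to 32/50 (64%) or 18/30 (60%) are non-significant. As a mean percentage of tasks with a true mean of 65%, the t-test is non-significant with these probabilities (SDs assumed):

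| SD | n = 50 | n = 30 |
|---|---|---|
| 20 | 0.07 | 0.25 |
| 30 | 0.36 | 0.58 |
| 35 | 0.49 | 0.67 |

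**Denominators.** Working back from 60 randomised at the SAP's own rates: 60/0.80 = 75 consented; 75/0.80 ≈ 94 eligible; 93.75/0.70 ≈ 134 positive screens. For 45 randomised the figures are about 56, 70 and 100. None of these groups is the 50 or 30 app recipients.

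**Proposed rule for retention.** Met if the estimate is at least 80%; not met if the exact 95% CI lies wholly below 80%; otherwise uncertain. At n = 50 the cut-offs are 40 or more and 33 or fewer; at n = 30 they are 24 or more and 18 or fewer.

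| True rate | n | Met | Uncertain | Not met |
|---|---|---|---|---|
| 70% | 50 | 0.08 | 0.61 | 0.32 |
| 70% | 30 | 0.16 | 0.68 | 0.16 |
| 80% | 50 | 0.58 | 0.40 | 0.01 |
| 80% | 30 | 0.61 | 0.38 | 0.01 |

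Rows may not sum to 1 because of rounding.

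**The case against.** **No pass rule is stated.** Nothing in either document equates a non-significant result with feasibility; the protocol speaks of exploring and informing. This stands. A reader might infer that the plan would pass a failing programme, or that the result settles whether a definitive trial follows, but the documents support neither inference. The defect is that a difference test is the only comparison described and no rule says how to read it.

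**The larger figures mix the documents.** The test is in the protocol, with 50 app patients; the SAP has 30 and omits the test. This also stands, so 0.57 and 0.28 are the figures for the plan as written.

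**The SAP already does much of this.** A reader of SAP 4.1 might infer that feasibility is assessed by satisfaction and usability scores alone. Table 2 shows otherwise. SAP 3.1 also names the three pre-randomisation denominators, and Table 2 leaves the arm columns blank for consent and randomisation. Of the protocol's own three measures, only randomisation lacks an app-recipient denominator. What remains is that the protocol wording conflicts with the SAP, and the SAP does not link its percentages to its benchmarks.

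**The remedy is slower to declare failure.** This is correct. The exact test finds 34/50 (p = 0.049) and 19/30 (p = 0.036) significantly below 80%, yet their exact upper limits are 0.805 and 0.801, so the rule calls both uncertain. At a true 70% the test falls significantly below the benchmark 43% (n = 50) or 27% (n = 30) of the time; the rule says not met 32% or 16% of the time.

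**Adherence may be less exposed.** With SD 20 and n = 50 the risk is small; with larger SDs or n = 30 it is not.

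**Conclusion.** The concern holds as a mismatch between the primary hypothesis and the stated test, together with a population that does not fit the randomisation rate or the eligibility and consent benchmarks. With 50 app patients, observed retention anywhere from 70% to 90% would be reported as not different from 80%, and a true rate of 70% would more often than not fall in that range (0.57). Reading the test the other way, with significance required to pass, works no better. The sizes depend on the assumed two-sided 5% level, the assumed true rates and, for adherence, the assumed SD.

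The protocol and SAP must be reconciled on how feasibility is compared with the benchmarks. The SAP's own position for Aim 2, that p-values are not recommended in small pilots and that estimates with intervals should be used, applies equally to Aim 1. This should be corrected before analysis.

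**What to change.** In protocol section 9 and in SAP 4.1 and Table 2:

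1. Replace the difference tests with the observed proportion and its exact 95% CI, shown beside each benchmark. If adherence is analysed as continuous, give the mean percentage of tasks with its 95% CI.
2. State the rule: met if the estimate is at or above the benchmark; not met if the whole CI is below it; otherwise below benchmark but uncertain.
3. Fix the denominators: positive screens, eligible and consented patients as in SAP 3.1; all randomised for retention (also by arm); everyone randomised to Arms 1 and 2 for adherence. Both documents list failure to access the app within a month of randomisation as an exclusion. If that were applied here, it would remove the least adherent patients.
4. Add an eligibility row to Table 2.

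The cost is wording and a few intervals, with no new patients or data. The price is indecision. At a true retention of 70% the chance of met is only 8% (n = 50) or 16% (n = 30), but the verdict is uncertain about 61% or 68% of the time. A programme truly at 80% is called met only about 60% of the time. The revised text should say so.

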### Sample Size and Power

This exploratory trial is not intended to test mCST's efficacy. While the 60-person sample size reflects the pragmatics of recruitment during a short enrollment period, it is large enough both to inform us about the potential challenges of delivering an app-based intervention in the context of post-discharge care as well as to provide meaningful confidence intervals for our estimates as was true for the similarly sized LIFT RCT (R34 AT00819).

## 10. Subject Participation Duration

Participating subjects in aim 1 will be asked to participate in a singular study visit lasting 30-60 minutes. Participating subjects in aim 2 will be asked to participate for up to a total of 3 months. Participating in this pilot, randomized RCT will require 1 month of daily, active participation in which the patient is practicing mCST daily and completing weekly check-ins. At the end of the 1 month (post T1 completion), the patient will be asked to complete T2 survey. Once the patient has completed the T2 survey, he/she is finished with active study participation for an additional 2 months at which time they will be asked to complete T3 survey. Patients will be given the option, between T2 and T3 completion, to continue to utilize the app and the mCST content; however, no weekly check-ins will be completed at this time.

## 11. Study Duration

For this project, Aim 1 (usability testing) is anticipated to take approximately 1-3 months to complete depending on rate of recruitment, user response to app usability, and required fixes to app based on user response.

As this project is centered around Aim 2 (pilot RCT), it is anticipated that from the initiation of Aim 2, that it will take 15 months to complete data collection (~12 months for cumulative enrollment with 3 months to complete all long-term follow up). From the time period of completing follow-up, it is estimated that it will take an additional 1-3 months for all final analyses to be completed for all Aims.

## 12. Risk-Benefit Assessment

### Potential risks

It is possible that participating patients could experience a breach of confidentiality should their records be accessed unlawfully by an outside party or general, inadvertent error. In addition, participants may experience mild anxiety when answering survey questions, though we have not observed this in similar interventions such as LIFT or CSTEP. However, we believe that involvement in this study will present no significant physical, psychological, financial, legal, or other risks.

### Adequacy of protection against risks:

#### Recruitment and informed consent procedures.

First, the Duke Institutional Review Board (IRB) will review and approve the study protocol before study initiation. Informed consent (e-consent or written) will be required from all participants, including content experts. Second, we will use a standardized screening and enrollment protocol that respects participant privacy and rights. The study team will only approach those patients that are deemed appropriate for the study, which will be determined by EMR review and/or conversations with the clinical team and/or PI. The approach of patients will be aided by a short IRB-approved recruitment video. The study team will then ask the patient to read and sign the study consent form at the time of enrollment. Potential subjects will be given as much time as they need to consider study participation. For Aim 2, we will take great care to present the treatment group assignment possibilities ("like drawing a number out of a hat") tactfully and with clearly stated equipoise in person or via phone utilizing the IRB approved telephone script, as we have done successfully in past clinical trials. A copy of the consent form will be given to participant and the original maintained in a secure location at the study site.

### Protections against risk

#### *General oversight*

There are several ongoing mechanisms for monitoring the occurrence of adverse events. The PI or delegated study team member will perform day-to-day monitoring of the study activities. Careful monitoring of all persons entering the study will minimize attrition and will ensure the clinical safety of these patients. A telephone number for the study team facilitates this monitoring and an email address ([[contact]](mailto:[contact])) provided to participants upon entry into the study to report concerns related to study participation.

#### *Plans to prevent coercion of patients and to ensure voluntary participation*

We will strive to create an environment free of any coercive practices for patients. We will stress that study involvement is voluntary and that choosing to participate or not participate will not affect their care in anyway. In addition, we will utilize the standardized 2-minute informational video, which has been used successfully in past trials describe treatment groups and ensure a similar approach across sites.

#### *Specific longitudinal participant oversight plans for severe psychological distress (including suicidal ideation)*

Given the difficult situations faced by patients, we recognize that there is a slight risk that some participants may become distressed completing questionnaires or viewing study materials, as mentioned above.

We will take the following measures to prevent any negative reactions as well as effectively manage any serious distress that occurs:

- (1) All of the in-person and telephone-based data collection sessions will be conducted by study team members who are sensitive to the issues that arise.

(2) Study team members will emphasize to participants that any interviews or other study interactions are participant-controlled. Thus, participants will be instructed that they are in control over what they share and generally how long they discuss any topic that is addressed.

(3) Participants will be told that they can discontinue an interview or telephone session at any time and that they are free to reschedule an interview or treatment session at any time within the week.

(4) Overall, we are very sensitive to the common and pervasive nature of psychological distress among cardiorespiratory failure survivors and are experienced in discussing these issues with them. There is also a potential risk for identifying underlying mental health issues through the mCST sessions, telephone calls, and survey responses. For issues such as passive suicidal ideation or symptoms of depression, anxiety, or PTSD, an informational sheet will be provided with contact numbers for additional mental health services.

Additionally, at the beginning of the program, all subjects will be informed that the training program may uncover unresolved and distressing thoughts or feelings; and a list of resources will be provided at that time.

### Suicidality Response Plan

Should a patient indicate to a study team member, thoughts of suicidality or ideation of suicidality, the Suicidality Response Plan could be activated.

If the participant is deemed to be at high risk based on direct interaction plus the C-SSRS item response, the delegated study team member will administer the C-SSRS to assess the participant to determine if they endorse active suicidal ideation. The trained staff will also determine if the participant is currently being treated by a mental health professional.

If the patient is deemed not to be actively suicidal, they will be given a list of local mental health resources as follows:

- Duke: Call Emergency Psychiatry at [contact] or [contact], available 24 hours a day, 7 days a week.
- The National Suicide Prevention Lifeline - [name] is a free, 24-hour hotline available to anyone in suicidal crisis or emotional distress.

If the participant is considered actively *suicidal* then at least one of the following plans will be followed depending on the location of the participant for each of the following situations:

- Situation 1
  - If the participant is with one of the study personnel, the study personnel will notify the site PI one of the other PIs immediately.
  - The study personnel will either physically walk the subject to the emergency department, or call a Psychiatric Emergency services number relevant to the site as described above.
- Situation 2
  - If the participant is on the telephone:
    - The study personnel will notify the site PI one of the other PIs immediately
    - The study personnel will stay on the telephone with the subject participant.
    - The study personnel will immediately contact 911 to initiate an on-site rescue if such action is clinically indicated.

- The study personnel will stay on the telephone with the subject until EMS services have contacted the participant.

If the participant is determined to be actively suicidal and require immediate medical therapy, they will be withdrawn from the study.

As described above, all concerns about participant safety will be discussed immediately with the PI - including concerning severe distress that does not involve suicidality.

For these situations, once an “alert situation” is known, the PI will refer the participant if needed (based on a PI-led phone call) to local psychological resources. The study team will also make urgent and emergency referrals as needed based on information learned.

To date based on some studies that have included over 400 participants, we have found that <5% of participants will require a call from the PI during some point in the study period. Of those, none has required referral to acute psychiatric care after a detailed interview from the PI. After a disposition / solution has been made, both the resolution (and follow up) will be documented in the ‘contact log’ section of the data system for reporting to the DSMB.

